# 4.7 Removal of Patients from Protocol Therapy

Subjects will be removed from therapy when any of the criteria listed in Section 5.5 apply. Notify the Principal Investigator, and document the reason for treatment discontinuation and the date of discontinuation. The subject should be followed-up per protocol.

#### 4.8 Subject Replacement

Subjects missing 7 or more doses due to toxicity will not be replaced since these subjects will be considered to have experienced a dose limiting toxicity.

### 5.0 STUDY PROCEDURES

# 5.1 Screening/Baseline Procedures

Assessments performed exclusively to determine eligibility for this study will be done only after obtaining informed consent. Assessments performed for clinical indications (not exclusively to determine study eligibility) may be used for baseline values even if the studies were done before informed consent was obtained.

All screening procedures must be performed within 90 days prior to registration unless otherwise stated. The screening procedures include:

#### 5.1.1 Informed Consent

#### 5.1.2 Medical history

Complete medical and surgical history, history of infections

### 5.1.3 Demographics

Age, gender, race, ethnicity

# 5.1.4 Review subject eligibility criteria

# 5.1.5 Review previous and concomitant medications

# 5.1.6 Physical exam including vital signs, height and weight

Vital signs (temperature, pulse, respirations, blood pressure), height, weight

#### 5.1.7 Performance status

Performance status evaluated prior to study entry according to Appendix II.

#### 5.1.8 Adverse event assessment

Baseline adverse events will be assessed. See section 7 for Adverse Event monitoring and reporting.

### 5.1.9 Hematology

#### 5.1.10 Blood draw for correlative studies

See Section 9.0 for details.

#### 5.1.11 Serum chemistries

Comprehensive metabolic panel (CMP) to include: albumin, alkaline phosphatase, amylase, lipase, ALT/SGPT, AST/SGOT, BUN, creatinine, electrolytes (sodium, potassium, calcium, chloride, bicarbonate), glucose, and total bilirubin.

# 5.1.12 Pregnancy test (for females of child bearing potential)

See section 3.1.12 for definition.

#### 5.1.13 Tumor assessment

# 5.2 Procedures During Treatment

# 5.2.1 Concurrent phase

- · Physical exam including vital signs
- Performance status
- Adverse event assessment
- Serum chemistries (amylase and lipase do not need to be resulted prior to treatment administration in the absence of clinical symptoms)
- Adrenal function test and thyroid function test
- · Optional blood collection

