# 2.2 Secondary Objectives

- 2.2.1 To assess the safety and tolerability of concurrent durvalumab and radiotherapy compared to historical data from patients treated with standard of care chemoradiation;
- 2.2.2 To determine the overall survival (OS) defined as the time from study enrollment to death due to any cause;
- 2.2.3 To determine the distant metastases-free survival defined as the time from the study enrollment to any new distant lesion;
- 2.2.4 To determine the local and regional control defined as the time from the study enrollment to any local and regional lesion;

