# 4.2 Toxicities and Dosing Delays

Any subject who receives treatment on this protocol will be evaluable for toxicity. Each patient will be assessed for the development of toxicity according to the Time and Events table (section 5.4) Toxicity will be assessed according to the NCI Common Toxicity Criteria for Adverse Events (CTCAE), version 5.0. There are no durvalumab dose modifications. However, durvalumab doses may be delayed or omitted. Dosing decisions and toxicity management should be made according to the system showing the greatest degree of toxicity as indicated in the toxicities and management algorithms (Appendix I).

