# 4.4.12 Radiation Therapy Adverse Events

Reversible or permanent alopecia, bone marrow toxicity, skin pigmentation, and esophagitis are expected side effects of radiation therapy.

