# 5.3 Follow-up Procedures

- Follow up visit every 3 months for 2 years; every 6 months for years 3-5; then yearly Procedure
- Physical exam including vital signs
- Performance status
- Adverse event assessment
- Complete blood count and serum chemistries
- Adrenal function tests and thyroid function tests
- Chest CT include adrenals

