# ASSESSMENTS DURING CONCURRENT TREATMENT

Assessments	Weekly (+/- 3 days)	At week 1 and 5 only (+/- 7 days)
Performance status	X	
CMP	X 	
Thyroid function test		X
Adrenal function test		X
Rad Onc Evaluation	X	
Med Onc evaluation		X 
Adverse event evaluation	X	
Specimen collection for banking		$X_3$

<sup>1 Biweekly

<sup>2 Testing does not need to be repeated if performed within 7 days of starting protocol therapy.

<sup>3Day 1 and Day 42

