#### Other-Immune-Mediated Reactions

Severity Grade of the Event Refer to NCI CTCAE applicable version in study protocol for defining the CTCAE grade/severity)	Dose Modifications	Toxicity Management
Any Grade	Note: It is possible that events with an inflammatory or immune mediated mechanism could occur in nearly all organs, some of them are not noted specifically in these guidelines (e.g. immune thrombocytopenia, haemolytic anaemia, uveitis, vasculitis).	Patients should be thoroughly evaluated to rule out any alternative etiology (e.g., disease progression, other medications or infections).  The Clinical Study Lead may be contacted for immune-mediate reactions not listed in the "specific immune-mediated reactions' section  Consultation with relevant specialist  Treat accordingly, as per institutional standard.
Grade 1	No dose modifications.	Monitor as clinically indicated
Grade 2	Hold study drug/study regimen until resolution to ≤Grade 1 or baseline.      If toxicity worsens, then treat as Grade 3 or Grade 4.      Study drug/study regimen can be resumed once event stabilizes to Grade ≤1 after completion of steroid taper.      Consider whether study drug/study regimen should be permanently discontinued in Grade 2 events with high likelihood for morbidity and/or mortality when they do not rapidly improve to Grade <1 upon treatment with systemic steroids and following full taper.	For Grade 2, 3, or 4  Treat accordingly, as per institutional standard, appropriate clinical practice guidelines, and society guidelines. (See page 4).
Grade 3	Hold study drug/study regimen until resolution to Grade ≤1 or baseline	
Grade 4	Permanently discontinue study drug/study regimen	

Note: As applicable, for early phase studies, the following sentence may be added: "Any event greater than or equal to Grade 2, please discuss with Clinical Study Lead."

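### No blood count is scheduled during concurrent durvalumab/RT, and none is listed for consolidation, so on-treatment haematological toxicity is not systematically measured

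*Combined protocol and SAP*

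**What the plan says.** Section 4.2 makes the schedule in section 5.4 the basis for measuring toxicity: "Each patient will be assessed for the development of toxicity according to the Time and Events table (section 5.4".

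On treatment, the blood safety tests in sections 5.2.1 and 5.2.2 are thyroid and adrenal function and "Serum chemistries (amylase and lipase do not need to be resulted prior to treatment administration in the absence of clinical symptoms". Section 5.1.11 defines the chemistry panel as "Comprehensive metabolic panel (CMP) to include: albumin, alkaline phosphatase, amylase, lipase, ALT/SGPT, AST/SGOT, BUN, creatinine, electrolytes", followed by glucose and total bilirubin. It contains no cell count. The section 5.4 table headed "ASSESSMENTS DURING CONCURRENT TREATMENT" and the consolidation table each carry a CMP row and no CBC row.

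CBC is scheduled on either side of treatment. Haematology is a screening item (5.1.9), with a 30-day window before registration in the pre-treatment table. Section 5.3 lists "Complete blood count and serum chemistries" for follow-up, and the follow-up table agrees.

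The protocol names haematological risks in several places:
- Section 4.4.12: "Reversible or permanent alopecia, bone marrow toxicity, skin pigmentation, and esophagitis are expected side effects of radiation therapy".
- Section 1.2 puts anaemia among the events seen in at least 10% of durvalumab monotherapy patients.
- Section 7.2.1 includes haematological events in the list of adverse events of special interest.
- Appendix I, under other immune-mediated reactions, gives as examples "immune thrombocytopenia, haemolytic anaemia, uveitis, vasculitis".

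**The concern.** Entry depends on neutrophil, platelet and haemoglobin thresholds (section 3.1.9), but no count is then required during radiotherapy. A cytopenia is by definition a finding on a blood count. Without a scheduled one, detection depends on symptoms or on a clinician choosing to order the test, and mild or silent cases are the ones most easily missed.

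This bears on a stated objective: "To assess the safety and tolerability of concurrent durvalumab and radiotherapy compared to historical data from patients treated with standard of care chemoradiation". Section 1.4 also hypothesises that the regimen will be better tolerated. If events are missed because counts were not taken, the observed rate falls for a reason unrelated to the treatment, and the error runs in the direction of the hypothesis. The same incomplete data would feed the twice-yearly interim reports (10.3.4) and the quarterly adverse event review (11.4). The grade-based actions in Appendix I could not be applied consistently to cytopenias.

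**Working it through.** **1. The schedule entries side by side**

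| Place | Phase | CBC? |
|---|---|---|
| 5.1.9; pre-treatment table in 5.4 | Screening | Yes |
| 5.2.1 | Concurrent | No |
| Concurrent table in 5.4 | Concurrent | No (CMP biweekly) |
| 5.2.2 | Consolidation | No |
| Consolidation table in 5.4 | Consolidation | No (CMP at each monthly infusion) |
| 5.3; follow-up table in 5.4 | Follow-up | Yes |

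All four on-treatment entries omit it, and all the others include it.

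**2. Scheduled counts on each reading**

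Radiotherapy is 30 fractions. At an assumed five per week, that is 30/5 = 6 weeks, with no scheduled CBC.

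Consolidation lasts up to one year. By its own list and table, the count is again zero. However, section 4.6 and the follow-up table start the 3-monthly visits at the end of concurrent durvalumab/RT, not at the last dose. If those visits overlap a full year of consolidation, CBCs fall at about months 3, 6, 9 and 12, so about four. The first would then come 6 weeks plus 3 months after radiotherapy starts, which is about 1.4 + 3 = 4.4 months.

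**3. Scale of one named risk**

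Table 1 in section 1.2 gives anaemia in the reference trial. The percentages reproduce:
- Durvalumab: 36/475 = 7.6% any grade, 14/475 = 2.9% grade 3-4.
- Placebo: 25/234 = 10.7% any grade, 8/234 = 3.4% grade 3-4.

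At the durvalumab rates, 50 patients would give 50 × 36/475 = 3.8 any-grade and 50 × 14/475 = 1.5 grade 3-4 cases. The chance of at least one grade 3-4 case is 1 − (461/475)^50 = 0.78. These figures describe occurrence, not cases missed.

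**4. What the planned analysis can and cannot show**

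Section 10.3.2 plans a toxicity rate with an exact binomial interval. That interval covers sampling error only. Zero events in 50 gives an upper 95% limit of 1 − 0.025^(1/50) = 7.1%, whether or not counts were taken.

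As an illustration, observed rate = true rate × proportion ascertained. The documents give neither input, so both are assumed:

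| True rate | 25% found | 50% found | 75% found |
|---|---|---|---|
| 10% | 2.5% | 5% | 7.5% |
| 20% | 5% | 10% | 15% |
| 30% | 7.5% | 15% | 22.5% |

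With a true rate of 20% and half the events found, the report would be 5/50 = 10% (exact 95% CI 3.3% to 21.8%). With all found it would be 10/50 = 20% (10.0% to 33.7%).

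**The case against.** Four stronger conclusions are tempting, and the case against each is sound.

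- **That there is no CBC through the whole of treatment.** A reader might infer this from the consolidation list and table. The follow-up clock starts at the end of concurrent durvalumab/RT, and the imaging footnote is the same in the consolidation and follow-up tables, which suggests overlapping schedules. Against that, the two tables both list examination, performance status, adverse event evaluation and CT, which would be largely redundant if they ran together. The text does not settle it.
- **That haematological toxicity goes unmeasured, or is found only once symptomatic.** Adverse event evaluation is weekly in radiotherapy and monthly in consolidation. Section 7.2.1 counts laboratory abnormalities of clinical significance as adverse events. Nothing bars a CBC ordered in routine care. The gap is in systematic measurement.
- **That the safety comparison is biased by a known amount.** Section 10.3.2 plans a one-sample rate of events at least possibly related to treatment. No historical haematological rate, comparison method or comparator testing frequency is given.
- **That the anaemia counts in step 3 estimate cases missed.** The reference patients had just finished chemoradiation, whereas these patients receive none of its chemotherapy. The placebo rates in the same table are higher than the durvalumab rates. Table 1 is also not shown to be limited to treatment-related events, as section 10.3.2 is.

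It is also fair that Appendix I names the cytopenias only as examples in a catch-all section, and that section 7.2.1 places haematological events among the rarer responses. They are nevertheless named risks, and radiation marrow toxicity is called expected. The absence of any scheduled count during radiotherapy stands on every reading.

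**Conclusion.** The point holds in a limited form. No CBC is scheduled during concurrent durvalumab/RT. In consolidation none is listed, and whether any falls there depends on an overlap with follow-up that the protocol neither states nor excludes. On-treatment haematological toxicity is therefore not systematically measured, and asymptomatic laboratory-defined events will probably be under-counted.

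The likely direction favours the study regimen under objective 2.2.1. This assumes that the historical chemoradiation patients had counts taken more regularly, which the documents do not state. The size cannot be calculated. The anaemia figures show only that such events are plausible in 50 patients, and the ascertainment table rests on assumed inputs. The primary endpoint is not affected. This is a worthwhile, inexpensive correction to the safety data, not a flaw that undermines the trial.

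**What to change.** Reconcile the on-treatment entries (5.2.1, 5.2.2 and the concurrent and consolidation tables in 5.4) with the screening and follow-up entries (5.1.9, 5.3 and their tables) by adding a CBC to the on-treatment lists and tables. Blood is already drawn for the CMP in both phases, so existing draws can be used. The testing frequency is for the investigators to set.

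State in section 4.6 or 5.3 whether follow-up visits, with their CBC, run during consolidation or begin after it.

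The cost is a short amendment, a small laboratory charge and more low-grade laboratory adverse events to record. Counts that were not taken cannot be recovered at analysis, so the change helps only patients treated after it is made.

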# 5.2.2 Consolidative phase

- · Physical exam including vital signs
- Performance status
- Adverse event assessment
- Serum chemistries (amylase and lipase do not need to be resulted prior to treatment administration in the absence of clinical symptoms)
- · Adrenal function tests and thyroid function tests
- · Chest CT include adrenals
- Pulmonary function testing (PFT/DLCO)
- · Optional blood collection

# 5.3 Follow-up Procedures

- Follow up visit every 3 months for 2 years; every 6 months for years 3-5; then yearly Procedure
- Physical exam including vital signs
- Performance status
- Adverse event assessment
- Complete blood count and serum chemistries
- Adrenal function tests and thyroid function tests
- Chest CT include adrenals

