## 4.6 Duration of Follow Up

Subjects will be followed every 3 months until 2 years post concurrent durvalumab/RT then every 6mos during year 3-5, then yearly or until death, whichever occurs first.

Subjects who discontinue for reasons other than progressive disease will have post-treatment follow-up for disease status until disease progression, initiating a non-study cancer treatment, withdrawing consent or becoming lost to follow-up. After documented disease progression each subject will be followed for overall survival until death, withdrawal of consent, or the end of the study (whichever occurs first). Subjects removed from treatment for unacceptable adverse events will be followed until resolution or stabilization of the adverse event.

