#### ASSESSMENTS DURING CONSOLIDATIVE DURVALUMAB TREATMENT

Assessments	Every month at infusion	Every 3 months
Physical examination including vital signs (blood pressure, weight)	X	
Zubrod performance status	X	
CMP	X	
Thyroid function (TSH, T3 and T4);		Every 2 months
AM cortisol, ACTH		Every 2 months
Serum or urine Pregnancy test	X 	
AE evaluation	X	
CT of chest with contrast and include adrenals		X 
Pulmonary function testing (PFTs/DLCO)		X 
Blood collection for banking		X 

<sup>1 Every 6 weeks

<sup>2After completion of concurrent durvalumab/radiotherapy, radiographic assessment with CT chest with contrast including adrenals will occur within 2 weeks. Further radiographic assessment will occur every 3 months for 2 years. After 2 years, radiographic disease assessment should be performed every 6 months during year 3-5 then annually thereafter. FDG-PET/CT should be done to confirm clinically uncertain progression or treatment related effects at the discretion of the treating investigator. This imaging may be done locally.

<sup>3At 6 months only.

<sup>4At 12 weeks and end of the study.

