#### Late Adverse Events (as applicable)

Adverse events occurring in the time period from the end of acute monitoring, to 5 years post treatment, will be defined as late adverse events. Immune-mediated adverse events such as adrenal insufficiency, hypothyroidism/thyroiditis, hyperthyroidism, hypophysitis, diabetes mellitus, nephritis and renal dysfunction will be monitored by medical oncology and other specialists during follow up visit whereas radiation side effects will be monitored by radiation oncology.

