# Other events requiring reporting Hepatic function abnormality

Hepatic function abnormality that fulfills the biochemical criteria of a potential Hy's Law case in a study patient, with or without associated clinical manifestations, is required to be reported as "hepatic function abnormal" within 24 hours of knowledge of the event to the sponsor and AstraZeneca Patient Safety using the designated Safety e-mailbox (see Section 10.3.2 for contact information), unless a definitive underlying diagnosis for the abnormality (e.g., cholelithiasis or bile duct obstruction) that is unrelated to investigational product has been confirmed. The criteria for a potential Hy's Law case is Aspartate Aminotransferase (AST) or Alanine Aminotransferase (ALT) ≥3x Upper Limit of Normal (ULN) together with Total Bilirubin (TBL) ≥2xULN at any point during the study following the start of study medication irrespective of an increase in Alkaline Phosphatase (ALP).

- If the definitive underlying diagnosis for the abnormality has been established and is unrelated to investigational product, the decision to continue dosing of the study patient will be based on the clinical judgment of the investigator.
- If no definitive underlying diagnosis for the abnormality is established, dosing of the study patient must be interrupted immediately. Follow-up investigations and inquiries must be initiated by the investigational site without delay.

Each reported event of hepatic function abnormality will be followed by the investigator and evaluated by the sponsor and AstraZeneca/MedImmune.

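### Follow-up laboratory tests: Section 5.3 requires thyroid, adrenal and serum chemistry tests, but the follow-up table schedules only a CBC and a BMP, so asymptomatic late events could be missed

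*Combined protocol and SAP*

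**What the plan says.** Section 5.3 sets follow-up visits every 3 months for 2 years, every 6 months in years 3-5, and yearly after that. Its list of procedures includes "Complete blood count and serum chemistries" and "Adrenal function tests and thyroid function tests". Section 4.6 gives the same schedule: "Subjects will be followed every 3 months until 2 years post concurrent durvalumab/RT then every 6mos during year 3-5, then yearly".

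The follow-up table in Section 5.4 uses that schedule as its single column. It has seven rows: history and physical, performance status, tumor measurement, medical oncology exam, AE evaluation, one laboratory row (CBC and BMP), and chest CT. Its only footnote concerns imaging.

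Three other places bear on the point:

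- Section 5.1.11, headed as serum chemistries, defines them as a "Comprehensive metabolic panel (CMP) to include: albumin, alkaline phosphatase, amylase, lipase, ALT/SGPT, AST/SGOT", and continues through creatinine, electrolytes, glucose and total bilirubin.
- Section 4.2 says: "Each patient will be assessed for the development of toxicity according to the Time and Events table (section 5.4".
- Section 7.2.1 defines late adverse events as those from the end of acute monitoring to 5 years post treatment. It adds: "Immune-mediated adverse events such as adrenal insufficiency, hypothyroidism/thyroiditis, hyperthyroidism, hypophysitis, diabetes mellitus, nephritis and renal dysfunction will be monitored by medical oncology" and other specialists at follow-up visits. It names no laboratory test.

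**The concern.** Two current lists for the same visits disagree, and the protocol does not rank them. Because Section 4.2 points to the Time and Events table for toxicity, a coordinator working from that table would order no thyroid, cortisol or ACTH test once durvalumab has ended. If BMP has its usual meaning, liver enzymes, bilirubin, amylase and lipase would also go unmeasured.

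Safety and tolerability is a secondary endpoint. Section 10.3.2 summarises it as a toxicity rate with an exact binomial interval. Section 7.2.1 counts clinically significant laboratory findings as adverse events, and it names endocrinopathies, transaminase rises and lipase or amylase rises as events of special interest. An asymptomatic late event that nobody tests for never enters that rate. If some staff follow Section 5.3 and others the table, late events are also ascertained unevenly across patients.

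**Working it through.** The plan states no figure to reproduce. The check compares the schedules and then counts visits.

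**1. Laboratory tests by phase (Sections 5.3 and 5.4)**

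| Source | Chemistry | Thyroid | Adrenal |
|---|---|---|---|
| Pre-treatment table | CMP | yes | AM cortisol, ACTH |
| Concurrent table | CMP | yes (weeks 1 and 5) | yes (weeks 1 and 5) |
| Consolidation table | CMP | TSH, T3, T4 every 2 months | AM cortisol, ACTH every 2 months |
| Follow-up, Section 5.3 text | serum chemistries | yes | yes |
| Follow-up table | BMP | none | none |

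Only the follow-up table drops the thyroid and adrenal tests, which suggests an oversight rather than a decision.

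**2. Meaning of serum chemistries.** Section 5.1.11 equates the term with a CMP that includes amylase and lipase. Sections 5.2.1 and 5.2.2 use the same term, with a remark on amylase and lipase results, and the matching treatment tables show CMP. Reading it the same way in Section 5.3 is an inference, though a well-supported one. The protocol does not define BMP, so what it leaves out is an assumption. The thyroid and adrenal conflict depends on neither point.

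**3. Visits at which the lists differ.** Assumptions: consolidation ends about 12 months after radiotherapy, the patient stays in follow-up to year 5, every listed test is due at every visit, and later yearly visits are not counted.

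- Full year of durvalumab: year 2 gives 12/3 = 4 visits and years 3-5 give 36/6 = 6. Total 4 + 6 = 10.
- Durvalumab stopped at the end of radiotherapy: the first 2 years give 24/3 = 8 and years 3-5 give 6. Total 8 + 6 = 14.

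**4. Kind of event at stake.** In the protocol's Table 1 (durvalumab arm of the cited trial), hypothyroidism was 55/475 = 11.6% at any grade and 1/475 = 0.2% at grade 3 or 4. The grade 3-4 share is 1/55 = 1.8%. These are counts for the whole arm and are not split by time of onset. They indicate that such events are mostly low-grade, not how many would arise in follow-up.

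**5. Effect on the safety summary.** If all 50 planned patients are treated, each patient with an undetected treatment-related event lowers the rate for that event by 1/50 = 2 percentage points. How many patients that would be cannot be derived from the documents.

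**The case against.** The strongest reply is that the two lists can both be followed. The table omits the tests but does not forbid them, and Section 11.5 requires the study to be run exactly as the protocol describes, so staff who read the whole protocol would draw them. That is true, but Section 4.2 names the table as the guide for toxicity assessment, so relying on it is a foreseeable reading, and it departs from Section 5.3.

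Further objections, and what stands of each:

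- A BMP is itself a serum chemistry panel, so chemistries are narrowed rather than absent. This stands. The chemistry part is weaker than the thyroid and adrenal part.
- Section 5.3 attaches its frequency to the visit and not to each test, and in consolidation some listed tests are less frequent than the visits. This stands as a caution on the count of 10 to 14. Still, the follow-up table has one column and gives no other frequency for laboratory tests.
- Section 7.2.1 already assigns late endocrine and renal monitoring to clinicians. That helps with symptomatic events, but it names no test.
- The Hy's Law rule in Section 7.3.2 concerns reporting and sets no testing schedule. This stands. The rule is only minor support, in that its criteria apply throughout the study and need ALT or AST and bilirubin.
- The conflict could be removed by cutting Section 5.3 back to match the table. That would be consistent, but Section 7.2.1 would then have no scheduled test behind it.

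**Conclusion.** The concern holds. Section 5.3 and the follow-up table conflict on thyroid and adrenal tests, and, on the CMP reading of serum chemistries, on liver and pancreatic enzymes as well. Following the table omits required tests at about 10 to 14 visits per patient up to year 5, under the assumptions given with the count.

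The consequence is limited. Symptomatic events would still surface through the history, exams and AE evaluation that the table keeps, and a usual BMP still covers creatinine and glucose. The loss is in asymptomatic, mostly low-grade late events. It should be corrected because it bears on patient safety and on a secondary endpoint. It is not a threat to the main result: primary PFS is unaffected.

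**What to change.** In the follow-up table of Section 5.4:

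1. Replace BMP with CMP, using the panel in Section 5.1.11, and keep the CBC.
2. Add a row for thyroid function (TSH, T3 and T4).
3. Add a row for AM cortisol and ACTH.

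Schedule all three at the visits already planned: every 3 months to 2 years, every 6 months in years 3-5, then yearly. If the sponsor wants any test less often, the same frequency should be written in both Section 5.3 and the table.

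The cost is three entries in one table. No visits are added, and Section 5.3 already lists the tests. The burden is extra blood tests where staff had worked from the table alone, with a morning draw for cortisol.
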